## 1.0 Project Summary/Abstract

Depression and anxiety are the leading causes of disability and lost productivity, and are often underdiagnosed and undertreated owing to access, cost, and stigma barriers. Novel and scalable psychotherapies are urgently needed. Advances in artificial intelligence (AI) offer a transformative opportunity to develop intelligent voice assistants as virtual health agents accessible on personal devices. Meanwhile, major advances in human neuroscience have fueled a paradigm shift to study brain mechanisms underlying behavioral health interventions. Leveraging emerging science in these transdisciplinary areas, this project aims to develop and rigorously test a novel voice-enabled, AI virtual agent named Lumen, trained on Problem Solving Therapy (PST), for patients with moderate, untreated depressive and/or anxiety symptoms. The project will investigate the effect of Lumen on engagement of a priori neural targets—amygdala for emotional reactivity and dorsal lateral prefrontal cortex (DLPFC) for cognitive control—as putative mechanisms. The project has 2 phases: R61 and R33 (see Figure 1). Phase 1 is the R61 phase (years 1-2) and will be the sole focus of this protocol. Focusing on Lumen development and refinement as well as pilot testing, Phase 1 has 2 specific aims. Aim 1 on Lumen development and refinement will proceed in 2 stages: (1) scenario-based clinician evaluations, and (2) a formative user study (n=30 participants). Aim 2 is to pilot test Lumen in a 2-arm randomized clinical trial (pilot RCT), among 60 participants with moderate, untreated depression and/or anxiety who are randomized in a 2:1 ratio to receive PST with Lumen (n=40) on a secure study iPad or be on a waitlist (n=20). At weeks 0 and 16 participants will complete functional magnetic resonance imaging (fMRI) to assess neural target engagement as well as validated surveys of patient-reported outcomes (PROs) (e.g., depressive and anxiety symptoms, functioning, quality of life). In addition, participants will complete ecological daily assessments of mood, stress, appraisal and coping for 7 days every 2 weeks during the 16-week follow-up period. The Phase 1 milestones are (1) establishing the functionality, usability, and treatment fidelity of Lumen; and (2) demonstrating feasibility, acceptability, and neural target engagement. Achieving these milestones will provide the basis for the future R33 phase (Phase 2) focused on examining target engagement and PROs in a larger 3-arm RCT by comparing Lumen with a waitlist control arm and an in-person PST arm. This protocol only focuses on the R61 phase.

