corresponding, validated emotional reactivity self-report measures and that this relationship may be significantly modified by group assignment. Similarly, we examine the regression change of the DLPFC activity from week 0 to 16 on change in self-reported measures of cognitive control (problem solving, dysfunctional attitudes) from week 0 to 16, controlling for baseline values of the self-reported measures and group assignment. We expect that the coefficient for the change in DLPFC activation is significant and positive in the direction of improvement in its corresponding, cognitive control validated self-report measures and that this relationship may be significantly modified by group assignment.

In addition, we will also conduct exploratory and secondary analyses. We will conduct an exploratory whole-brain analysis (1) to verify our *a priori* specification of neural targets, namely, amygdala for emotional reactivity and DLPFC for cognitive control, and (2) to identify any additional voxel clusters that are activated by our tasks and are associated with treatment response. Secondary analyses compare differences in discrete changes in PROs from week 0 to 16 and trajectories of change based on intensive time-series ecological measures between the Lumen and waitlist control groups. Analyses of the treatment effects on PROs employ the same *t* test approach as described above for testing Criterion 1 for target engagement. Furthermore, dosing analyses are conducted within the Lumen treatment group. The primary dosing analysis examines the relationship of neural target activation in the amygdala and DLPFC to the 4 measures of dose (number and length of PST sessions, fidelity-weighted number, and length of PST sessions). The secondary dosing analysis examines the relationship of patient-report outcomes, ecological end-of-day assessments, and measures of treatment progress (e.g., PHQ9 and GAD7 across PST sessions) to the same 4 measures of dose. Given neural target activation measures and PROs are obtained at weeks 0 and 16, these analyses focus on change over the full 16-week span of the study, whereas ecological end-of-day assessments and treatment progress measures are available for a total of 8 occasions each, and thus will be considered longitudinally.

Please see Appendix 3 for detailed power analysis and statistical analysis plan.

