#### ***B.3.b. Definitions of primary and secondary dose measures***

Two primary dose measures will be the number of PST sessions and the length of PST sessions (in minutes) that participants complete with Lumen. Secondary dose measures will be each of the 2 primary measures weighted by the level of treatment fidelity. All Lumen-based PST sessions will be recorded and independently rated for fidelity by 2 PST master trainers using the validated 7-item PST Adherence and Competence Scale (PST-PAC).

In psychotherapy outcome research, dose is typically defined as the number of sessions of therapy as it is a natural quantitative unit of treatment applicable across types of psychotherapy. In this study, we also include the length of sessions as a measure of dose because (1) it is possible that the number of sessions varies little among participants given the brevity and controlled delivery of the therapy and (2) session length is an important parameter for possible optimization of Lumen to improve participant engagement and efficacy. Note that these dose measures are defined at any stage of the treatment; for example, after 4 sessions have been offered, a participant might have attended 3 sessions (number) for a total of 118 minutes (length). In other words, the dose measures are time-related variables.

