Similarly, therapeutic fidelity is another important parameter for optimization in Lumen. In our view, it is a proxy to the strength of medicine and its use in this context adjusts the implied assumption that one session (or the same length of a session) equals one unit or dose, except that the strength (potency) of active ingredients in psychotherapy cannot be measured or standardized in the same way as that of a medication. Although the level of fidelity may be defined differently (e.g., with varying weights of the item scores), the ratio of raw total score to the maximum is simple and easy to interpret and there is no empirical support, to our knowledge, for an alternative. Alternative definitions may be explored using data from this study, especially if they would provide a more nuanced understanding of the need for optimization of Lumen. We will construct fidelity-weighted versions of the dose measures, number and length, in order to adjust doses for conformance to standard PST. Assessing dose in the multiple ways as we propose will allow us to determine which measure is most accurate and to be employed in Study 2. Also, our methodology and results will make an important contribution as assessing dose effects of novel digital health interventions on mechanisms such as brain targets is complex and understudied.

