#### ***B.3.c. Dosing analyses***

Dosing analyses will be conducted **within the Lumen treatment group**. The primary dosing analysis will examine the relationship of neural target activation in the amygdala and DLPFC to the 4 measures of dose (number and length of PST sessions, fidelity-weighted number and length of PST sessions). The secondary dosing analysis will examine the relationship of PROs, ecological end-of-day assessments, and measures of treatment progress (e.g., PHQ9 and GAD7 across PST sessions) to the same 4 measures of

dose. Note that given neural target activation measures and PROs are obtained at weeks 0 and 16, these analyses will focus on change over the full 16-week span of the study, whereas ecological end-of-day assessments and treatment progress measures are available for a total of 8 occasions each, and thus will be considered longitudinally.

**Neural targets:** The primary dosing analyses will consist in the separate regressions of change in activation from week 0 to 16 for the amygdala and DLPFC on each dose variable. This results in 8 separate regressions: amygdala on number of sessions, amygdala on length of sessions, amygdala on fidelity-weighted number, amygdala on fidelity-weighted length, and also DLPFC on the same 4 dose variables. Assumptions of linear regression will be verified and corrected through data transformation as needed. Our purpose is to identify variants of the dose variables with the strongest association (i.e., highest  $R^2$ ) with change over 16 weeks in the 2 neural targets. If the coefficient for dose in these regressions is positive and significant, it confirms that the dose variable is associated with higher change in neural target activation.

**Patient-reported outcomes:** Depression and anxiety symptoms, functioning, and health-related quality of life will be measured at week 0 and 16. Thus, the secondary dose analysis for PROs mirrors the primary analysis for neural targets. That is, change from week 0 to 16 in the PROs will be separately regressed on the 4 dose variants, resulting in separate PRO-dose measure regressions. As in the primary analysis, our purpose is to identify variants of the dose variables with the strongest association (i.e., highest  $R^2$ ) with change over 16 weeks in the PROs of interest.

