**Treatment progress measures:** To monitor treatment progress, symptoms (PHQ9, GAD7) and treatment acceptability (usability, user experience, and treatment alliance) will be measured in each PST session at weeks 1, 2, 3, 4, 6, 8, 10, and 12 (for a total of 8 occasions). Similar to the analyses of ecological measures as described above, we will implement polynomial and logarithmic models and compare model

fit using BIC. These regressions'  $R^2$ 's will allow us to examine in detail the relationship of treatment progress and cumulative dose, with fidelity-to-PST taken into account using the fidelity-weighted number and length of PST sessions. Additionally, as is common in psychotherapy in general, it is possible that not all participants will complete the full 8 sessions as some may drop out early owing to either lack of improvement or “enough” improvement based on self-assessment or yet other reasons related or unrelated to the treatment. Using the Good-Enough-Level (GEL) model, some studies of in-person psychotherapy showed that the rate of change varied as a function of treatment duration, namely, the rate of change (progress) was faster for patients attending fewer sessions but slower for those attending more sessions. In other words, patients may remain in treatment until they improve. To explore whether a similar pattern is present for Lumen PST, we will apply the GEL modeling approach by extending the polynomial models for treatment progress measures, in particular, PHQ9 and GAD7, to include a fixed effect of total treatment dose (e.g., total number of sessions) and interactions between total treatment dose and linear, quadratic, and cubic rates of change. Essentially, the GEL model is a stratified analysis that examines dose effects across strata of participants with similar treatment dose (e.g., similar number of sessions attended), as opposed to aggregate dose effects across all participants. Furthermore, we will conduct exploratory analyses of baseline characteristics in relation to the dose effects on neural targets, PROs, ecological measures, and treatment progress measures. We anticipate that baseline characteristics (e.g., severity at presentation, sex as a biological variable, sociodemographics) may be related to dosing estimates (e.g., via actual sessions completed). To explore these relationships, baseline characteristics and their interactions with dose measures will be added to the models as described above.

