#### **B.4. Intention to Treat (ITT) and Handling Missing Data**

Clinical trials such as the one proposed must face the issues of dropout and missing data. We have put in place a strong plan to ensure maximum retention of participants through the course of the study, with a projected 85% or greater retention (see the *Recruitment and Retention Plan*). Data missing completely at random (MCAR) may be analyzed “as is” without imputation, as it does not introduce bias into estimates and inferences. More commonly, data are missing at random (MAR) owing to covariate-dependent events (e.g., irregular work shifts, children’s illness, transportation, and scheduling foul-ups). Our primary analysis technique, linear mixed models, is robust for MAR and provides unbiased estimates of model parameters without imputation. (One may impute as well, but the benefit is usually modestly improved power rather than changes to conclusions.) The more serious concern for behavioral interventions is the possibility that data will be missing not at random (MNAR). This occurs when dropout or missingness is related to the level of the outcome of interest (e.g., a participant’s level of depression or anxiety). If treatment is working well and symptoms of depression and anxiety have lessened, then participants may feel continuation in treatment is not necessary or beneficial. They drop out or miss sessions because the treatment seems to have worked. On the other hand, if participants experience no improvement in symptoms, they may drop out or miss sessions because they are discouraged that the treatment seems not to have worked. In either case, the loss of data is related to the outcomes under study and has the potential to bias the study’s conclusion about the intervention. Handling the problem of MNAR is difficult. First, there is no test for the presence of MNAR (*vs.* MAR). Second, there are many possible underlying sources of MNAR and there is no guarantee that explorations of missing data patterns will clearly reveal those sources. Third, missing data imputation for MNAR necessarily makes strong and untestable statistical assumptions, so that conclusions from imputed MNAR datasets must remain tentative. This picture reinforces our strong commitment to participant retention (see the Study 1 *Recruitment and Retention Plan*).

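### Ranking four overlapping dose measures by highest R-squared, with no sign condition and no measure of uncertainty, cannot show which one is most accurate

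*Combined protocol and SAP*

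**What the plan says.** Section 9.0 states that "dosing analyses are conducted within the Lumen treatment group". Appendix 3, B.3.b defines the measures. Number of sessions and length in minutes are primary. Of the other two it says: "Secondary dose measures will be each of the 2 primary measures weighted by the level of treatment fidelity". The weight is the fidelity score divided by its maximum. B.3.b adds that assessing dose in these several ways "will allow us to determine which measure is most accurate and to be employed in Study 2".

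B.3.c then plans eight single-predictor regressions: change from week 0 to 16 in the amygdala and in the DLPFC, each on each of the four measures. It says: "Our purpose is to identify variants of the dose variables with the strongest association", and defines strongest as highest R-squared. The next sentence reads a positive, significant coefficient as confirming that the dose measure goes with greater change. The same R-squared aim is repeated for the patient-reported outcomes. Ecological and treatment-progress measures are related to the same four measures in longitudinal models.

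B.3.b and B.3.c give no interval for the ranking, no minimum gap or tie rule, and no rule for results that point to different measures.

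**The concern.** In a regression with one predictor the standardised slope is the correlation r, and R-squared is r². A slope of +0.4 and a slope of −0.4 both give 0.16, so the ranking cannot tell more improvement with more dose from less. The sentence on positive, significant coefficients is not written as a condition for being chosen. The plan itself cites a pattern that could reverse the slope, in studies of in-person psychotherapy: "the rate of change (progress) was faster for patients attending fewer sessions but slower for those attending more sessions".

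The four measures also overlap by construction. Minutes accumulate over sessions, and each weighted measure is its parent scaled by a fidelity ratio. With about 34 people, small differences in R-squared among such measures are largely sampling noise. At stake is whether the pilot can say that one measure is the most accurate and carry it into Study 2 on that ground.

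**Working it through.** **The plan's own count.** 2 targets × 4 measures = 8 regressions, as B.3.c states.

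**Sample size.** 40 are to be randomised to Lumen (Section 1.0), with "projected 85% or greater retention" (B.4). 40 × 0.85 = 34, the planning floor.

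**What 34 people can resolve for a single correlation** (two-sided 0.05, Fisher z where power is involved):
- Significance needs |r| > t/√(t² + 32), with t = 2.037 on 32 degrees of freedom: 2.037/√(4.149 + 32) = 0.339.
- Detectable with 80% power: tanh[(1.960 + 0.842)/√31] = tanh(0.503) = 0.465.
- Power at r = 0.4: Φ(0.4236 × √31 − 1.960) = Φ(0.399) = 0.655.

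The plan's only power figure for an association (N = 60, r = 0.4, power 0.80) belongs to Criterion 2 in both arms. It holds there: 47 would suffice, and power at 60 is 0.892. No figure is given for the dosing analysis. Separating overlapping predictors is harder than detecting one of them.

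**Simulation, base assumptions.** These are assumed, not given: n = 34; attendance just meeting the milestones in Section 3.0 (95% with at least 1 session, 80% with at least 4), with 40% completing all 8; about 39 minutes per session (118/3, from the worked example in B.3.b); between-person CV 25%; mean fidelity 0.8. Implied correlations are about 0.84 for number v minutes, 0.97 for number v weighted number, and 0.98 for minutes v weighted minutes. Number of sessions is the true driver, and the two targets have independent errors. There were at least 4,000 trials per setting.

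**Simulation, wider assumptions.** 20,000 trials per setting, n = 34, with different spreads of attendance, minutes and fidelity and different true drivers. Correlations run over 0.52-0.96 (number v length), 0.88-0.99 (number v weighted number) and 0.95-0.99 (length v weighted length).

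| True r | Correct pick, base | Correct pick, wider | Winner has negative slope, wider |
|---|---|---|---|
| 0 | – | 22-27% | 50% |
| 0.2 | 32-34% | 29-40% | 13-17% |
| 0.3 | 39-41% | 32-51% | 4-8% |
| 0.4 | 45-47% | 36-63% | 1-3% |
| 0.6 | 60% | 45-83% | 0-0.2% |

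A random choice among four is right 25% of the time. Ranges in the base column are repeat runs.

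**Agreement between targets** (base, r = 0.3): the same winner in 29-30% of trials, against 25% with no effect.

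**Gap between first and second:** median R-squared difference 0.012 at r = 0.3 (base); 0.009-0.036 at r = 0.4 (wider).

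**Higher attendance** (70% complete all 8, r = 0.3): correct pick 45%, agreement 32%, negative winner 7%.

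**All 40 retained** (wider, r = 0.4): correct pick 37-67%, against 36-63% at 34.

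**How far off a wrong pick is** (base, r = 0.3): the winner is number or weighted number in 67-70% of trials. In one run the chosen measure correlated 0.94 on average with the true driver.

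**The case against.** - **The choice is not a lottery.** A reader might infer that it is. The figures do not support that: 25% is approached only with no effect, or when all measures are almost identical and the effect is modest. At r = 0.4 to 0.6 the rule is clearly better than chance. This objection stands.
- **A wrong pick costs little when the measures overlap, and selection improves when they do not.** With four equally correlated measures and true r = 0.4, the correct pick rises from 34% at an inter-measure correlation of 0.98 to 79% at 0.3. This stands, and it limits the harm. No loss in Study 2 has been shown.
- **Sign is looked at.** The sentence after the R-squared aim does look for a positive, significant slope, and a winner that is significantly negative is rare: about 4-5% of trials with no effect, and under 0.5% at r of 0.2 or more. The early-improver pattern in B.3.c concerns the rate of change in treatment-progress measures, which the plan models separately. What remains is that sign is not a stated condition for selection.
- **The neural R-squared does not decide alone.** B.3.b refers to assessing dose in several ways, and the patient-reported and longitudinal results also bear on the choice. That stands, but no rule says how to combine them.
- **The primary and secondary labels do not clash.** One might read B.3.b (weighted measures secondary) against B.3.c (all four in the primary dosing analysis) as a contradiction. B.3.b orders the measures and B.3.c orders the analyses by outcome, so this is at most a matter of wording.
- **The inputs are assumed.** They are. B.3.b allows that number of sessions may vary little, and the Section 3.0 milestones apply to all Lumen participants rather than to completers. Hence the ranges.

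**Conclusion.** The concern holds in a limited form. Highest R-squared in about 34 people, with no sign condition and no uncertainty attached, cannot support naming one of four overlapping measures the most accurate. Under the assumed inputs the top-ranked measure is the true driver in about 40% of trials at r = 0.3 and 45% at r = 0.4 (32-51% and 36-63% over wider assumptions). These figures rest on attendance, minutes and fidelity spreads that the documents do not give. The overlap is well founded for each weighted and unweighted pair and less certain for number v length.

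A reader might infer that Study 2 would be built on a seriously wrong measure. The documents and the simulation do not show that: the pick is usually a close relative of the true driver. The harm is an unsupported conclusion. Severity is minor, because the dosing analysis does not enter Criterion 1, Criterion 2 or the feasibility milestones.

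**What to change.** In Appendix 3, B.3.c:

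1. Make only measures with a positive dose coefficient eligible for selection.
2. For each target separately, report a paired bootstrap interval (resampling participants and recomputing all four regressions) for the difference in signed standardised coefficient, or in R-squared, between dose measures. Keeping the targets separate fits Appendix 3, A, which treats them as separate inferential domains.
3. Call one measure more accurate only if that interval excludes zero. Otherwise state that the measures were not distinguishable.

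Soften the B.3.b sentence on Study 2 to match. State in advance which measure is carried forward when none can be distinguished. Number of sessions, which B.3.b describes as the usual definition, is one candidate, but this is the sponsor's choice. It has a price: if minutes is the true driver at r = 0.3, a gate that defaults to number, using coefficients averaged over the two targets, names minutes only about 14% of the time, against 37% for highest R-squared.

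The cost is SAP wording and a short bootstrap on data already collected. The downside is that the pilot will often report that the measures were not distinguishable.
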